5.2 Safety Analysis Set

The safety analysis set will consist of all subjects who received any QW formulation.

5.3 Handling of Missing Data

Data imputation will not be performed for missing data.

6 **Primary and Secondary Outcome Variables:**

Plasma drug concentrations and pharmacokinetics parameters of brexpiprazole after single or multiple administrations of the QW formulation.

7 Disposition and Demographic Analysis

7.1 Subject Disposition

The subject dispositions will be summarized for the single administration period (Cohort 1 and Cohort 1' [as necessary]) and the repeated administration period (Cohort 2).

The number of screened subjects will be presented. The numbers and percentages of following subjects will be summarized.

- For the single administration period (Cohort 1 and Cohort 1' [as necessary]):
 - 1) Subjects treated with conventional tablet
 - 2) Subjects withdrawn in period 1
 - 3) Subjects treated with QW formulation in period 2
 - 4) Subjects withdrawn in period 2
 - 5) Subjects treated with QW formulation in period 3
 - 6) Subjects completed in period 3
 - 7) Subjects withdrawn in period 3
 - 8) Subjects analyzed for PK
 - 9) Subjects analyzed for safety
- For the repeated administration period (Cohort 2):
 - 1) Subjects treated with conventional tablet
 - 2) Subjects withdrawn in period 1
 - 3) Subjects treated with QW formulation in period 2
 - 4) Subjects completed in period 2
 - 5) Subjects withdrawn in period 2
 - 6) Subjects analyzed for PK
 - 7) Subjects analyzed for safety

The denominators for each period are subjects treated with IMP in each period. The denominators for the analysis sets are subjects treated with QW formulation.

The numbers and percentages of subjects withdrawn in each period will also be summarized by primary reason for discontinuation.

Subjects who discontinue by the sponsor's circumstances and participate again will be counted once using final completion status. Listing of information regarding first discontinuation for these subjects will presented.

7.2 Demographic and Baseline Characteristics

Depending on data characteristics, frequency distribution or descriptive statistics of demographic and other baseline characteristics will be produced for the single administration period (Cohort 1 and Cohort 1' [as necessary]) and the repeated administration period (Cohort 2) based on PK and safety analysis sets.

Continuous variables (age, height, weight at screening, and BMI) will be summarized using summary statistics (mean, SD, min, median, max). Categorical variables (sex, race,

detailed ethnicity, country, medical history, complications and CYP2D6 phenotype) will be summarized by number and percentage of subjects.

For subjects who discontinue by the sponsor's circumstances and participate again, data at first screening will be used.

7.3 Medical History

Listing of medical history will be presented.

7.4 Treatment Compliance

Information for administration of IMP is described in Section 7.1 and 9.1.

7.5 Prior and Concomitant Medications

Medications will be coded using World Health Organization Drug Dictionary (WHO-DD) version Sep 2019 Global B3. Listing of prior and concomitant medication will be presented.

7.6 Protocol Deviations

A listing of major protocol deviations will be presented.

8 Efficacy Analysis

Not applicable.

9 Safety Analyses

Each safety endpoint will be summarized for each dose (Periods 2 and 3) of the QW formulation in the single administration period (Cohort 1 and Cohort 1' [as necessary]) and for the repeated administration period (Cohort 2) based on safety analysis set.

The baseline for statistical analysis is defined as data measured immediately prior to IMP administration in Period 2.

Adverse events (AEs) in each period are defined as AEs occurred on or after the IMP administration in each period to before the IMP administration in next period or the end of study.

Potentially clinically significant (potentially clinically significance [PCS]) abnormalities in each period will include the values measured on or after the IMP administration in each period to before the IMP administration in next period or the end of study.

9.1 Extent of Exposure

For the repeated administration period (Cohort 2), the number of administrations will be summarized using frequency distribution.

9.2 Adverse Events

All AEs will be coded by system organ class (SOC) and Medical Dictionary for Regulatory Activities (MedDRA version 23.1) preferred term (PT). If multiple occurrences of the same event are observed in the same subject during the same period, the highest severity will be used for analysis. The incidence of the following events will be summarized by SOC and PT:

- AEs occurring after administration of the QW formulation (treatment-emergent adverse events [TEAEs])
- TEAEs by severity
- TEAEs with an outcome of death
- Serious TEAEs
- TEAEs leading to discontinuations of the trial
- TEAEs by onset time (1-7 and 8-14 for Cohort 1 and Cohort 1' [as necessary]; 1-7 8-14, 15-21, 22-28, 29-35, 36-42 for Cohort 2)

The above summaries will also be prepared for TEAEs potentially causally related to the IMP.

Incidences of the AEs occurring in period 1 will be summarized by SOC and PT for subjects treated with conventional tablet.

9.3 Clinical Laboratory Data

Descriptive statistics of actual measurements and changes from baseline of laboratory test parameters (excluding qualitative urinalysis) at each time point will be produced.

For each laboratory parameter (excluding qualitative parameters), measurements will be classified as "lower than the lower limit of the reference range," "within the reference range," and "higher than the upper limit of the reference range" using the reference range specified by the central laboratory, and a shift table from baseline will be produced.

For qualitative laboratory parameters, a shift table from baseline will be produced.

The number and percentage of subjects with PCS laboratory test abnormalities will be determined. The criteria of PCS laboratory test abnormalities are provided in Appendix 1.

The number and percentage of subjects with abnormal changes in liver function (Hy's Law cases) will be determined.

Definition of Hy's Law Cases:

ALT or AST >= 3xULN (or Baseline) and Bilirubin (total) >= 2xULN or Baseline

9.4 Vital Sign Data

Descriptive statistics of actual measurements and changes from baseline of each parameter at each time point will be produced.

The number and percentage of subjects with PCS in vital signs and weight will be determined. The criteria of PCS vital sign abnormalities are provided in Appendix 2.

9.5 Physical Examination Data

Physical examination findings will be listed by subject.

9.6 Electrocardiogram Data

A shift table from baseline for normal/abnormal finding of 12-lead ECG will be produced.

Descriptive statistics of actual measurements and changes from baseline of each parameter at each time point will be produced.

The number and percentage of subjects with actual measurements of corrected QT interval (QTcF) at each time point being > 450 msec, > 480 msec, and > 500 msec will be determined. The number and percentage of subjects with changes from baseline being > 30 msec and > 60 msec will be determined.

Incidence of PCS ECG abnormalities will also be summarized. The criteria of PCS ECG abnormalities are provided in Appendix 3.

9.7 Other Safety Data

9.7.1 DIEPSS

For the DIEPSS total score (sum of items 1 to 8) and the score for each item, descriptive statistics of actual measurements and changes from baseline at each time point will be produced.

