3.7.5.8 Drug-induced Extrapyramidal Symptoms Scale

The investigator or subinvestigator will use DIEPSS at scheduled time points to assess the following 9 items on a 5-point scale from 0 (none, normal) to 4 (severe). The date and result of assessment will be recorded on the source documents and eCRF.

1. Gait	2. Bradykinesia	3. Sialorrhea	4. Muscle rigidity	5. Tremor
6. Akathisia	7. Dystonia	8. Dyskinesia	9. Global severity	

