4.3 Restricted Medications

The use of the following drugs between Day 1 of Period 1^{*} of each cohort and the completion of assessment on Day 14 of Period 3 in Cohort 1 or Cohort 1' (as necessary) (single administration period) or on Day 42 of Period 2 in Cohort 2 (repeated administration period) or the completion of ET assessment is restricted:

* For subjects who were withdrawn from the trial at the discretion of the sponsor and resume participation in the trial from Period 2 or 3, the use of the drugs is restricted from Day 1 of IMP administration in the treatment period (Period 2 or 3) in which they are to resume participation in the trial.

• Other antipsychotic drugs

The use of other antipsychotic drugs at a steady dose and regimen will be permitted within the dosing range indicated below. The dose or frequency may be reduced at the discretion of the investigator or subinvestigator in response to symptom improvement or maintenance or from a safety perspective. Upper limit of dose and regimen

- Antipsychotic medication comprising no more than two active components
- A daily dose equivalent to no more than 600 mg/day of chlorpromazine
 - If multiple antipsychotics are taken in the same day, this is to be the combined equivalent dose.

• Chlorpromazine equivalent doses are based on the conversion values listed in Appendix 5.

However, this does not include administration of antipsychotic medication at doses equivalent to less than 100 mg/day of chlorpromazine, which are not expected to have any antipsychotic effect.

• Antiparkinsonian drugs

The use of antiparkinsonian drugs will be permitted only when the subject has extrapyramidal symptoms and the investigator or subinvestigator concludes that these drugs should be used. In that case, the dose and regimen should comply with the package insert. However, preventive use will be prohibited. Therefore, subjects who have no extrapyramidal symptoms but are taking antiparkinsonian drugs at the time of informed consent must temporarily discontinue the medication. Extrapyramidal symptoms should be assessed using DIEPSS prior to new use or dose increase of an antiparkinsonian drug. It is not permitted for any antiparkinsonian drug to be administered within 12 hours prior to DIEPSS assessment.

• β-Blockers

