3.4 Trial Visit Window

Nominal time points will be used for summary of safety parameters and plasma concentration.

4 Sample Size

The target number of subjects is not based on a statistical hypothesis test. A simulation was performed with the PK model created based on PK data on the conventional tablet and QW-A formulation used in the QW-A formulation group in Trial 331-102-00021 conducted in Japan, and the probability that the mean plasma concentration of brexpiprazole after repeated administration of the QW-A formulation would be within the target range of concentration was determined. On the basis of this probability, the sample size was determined to be 20 subjects each for the single administration period (Cohort 1) and the repeated administration period (Cohort 2). Likewise, the sample size for an additional single administration period (Cohort 1') with a new dose was also determined to be 20 subjects.

5 Statistical Analysis Sets

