CT-12.1.1	Mean Change from Baseline in Electrocardiogram Results (Cohort 1)
CT-12.1.2	Mean Change from Baseline in Electrocardiogram Results (Cohort 1')
CT-12.1.3	Mean Change from Baseline in Electrocardiogram Results (Cohort 2)
CT-12.2.1	Shift Table of Electrocardiogram Findings (Cohort 1)
CT-12.2.2	Shift Table of Electrocardiogram Findings (Cohort 1')
CT-12.2.3	Shift Table of Electrocardiogram Findings (Cohort 2)
CT-12.3.1	Categorical Analysis of Electrocardiogram Parameters (Cohort 1)
CT-12.3.2	Categorical Analysis of Electrocardiogram Parameters (Cohort 1')
CT-12.3.3	Categorical Analysis of Electrocardiogram Parameters (Cohort 2)
CT-12.4.1.1	Incidence of Potentially Clinically Significant ECG Abnormalities (Cohort 1)
CT-12.4.1.2	Incidence of Potentially Clinically Significant ECG Abnormalities (Cohort 1')
CT-12.4.1.3	Incidence of Potentially Clinically Significant ECG Abnormalities (Cohort 2)
CT-12.4.2	Listing of Potentially Clinically Significant ECG Abnormalities
CT-13.1.1	Mean Change from Baseline in DIEPSS (Cohort 1)
CT-13.1.2	Mean Change from Baseline in DIEPSS (Cohort 1')
CT-13.1.3	Mean Change from Baseline in DIEPSS (Cohort 2)
CT-14.1.1	Columbia-Suicide Severity Rating Scale (C-SSRS) - Incidences of Suicidality (Cohort 1)

CT-14.1.2	Columbia-Suicide Severity Rating Scale (C-SSRS) - Incidences of Suicidality (Cohort 1')	
CT-14.1.3	Columbia-Suicide Severity Rating Scale (C-SSRS) - Incidences of Suicidality (Cohort 2)	
CT-15.1	Listing of Subjects whose CGI-S has Worsened	
CT-15.2	Listing of Subjects whose CGI-I has Worsened	
PKT-X.X.1.X	Individual and Summary of Plasma Concentration Following Single Administration	
PKT-X.X.2.X	Individual and Summary of Plasma Pharmacokinetic Parameters Following Single Administration	
PKT-X.X.3.X	Individual and Summary of Plasma Concentration Following Multiple Administration	
PKT-X.X.4.X	Individual and Summary of Plasma Trough Concentration Following Administration	
PKT-X.X.5.X	Individual and Summary of Plasma Pharmacokinetic Parameters Following Multiple Administration	
PKT-X.X.7.X:	Individual and Summary of Pharmacokinetic Parameter Ratios of QW Formulation to Conventional Tablet Following Oral Administration of OPC-34712	
PKF-X.X.1.X	Mean Plasma Concentrations Following Single Administration	
PKF-X.X.2.X	Median Plasma Concentrations Following Single Administration	
PKF-X.X.3.X	Plasma Concentrations Following Single Administration	
PKF-X.X.5.X	Mean Plasma Concentrations Following Multiple Administration	

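### DIEPSS is summarised only at scheduled visits, so a score taken between visits before antiparkinsonian rescue reaches no summary table; a worst-score row would close the gap cheaply

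*SAP*

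**What the plan says.** DIEPSS is a named safety endpoint (protocol 3.5.2). Protocol 4.3 sets the rescue rule: "The use of antiparkinsonian drugs will be permitted only when the subject has extrapyramidal symptoms", with the investigator's agreement. It adds: "Extrapyramidal symptoms should be assessed using DIEPSS prior to new use or dose increase of an antiparkinsonian drug". It also protects later scores from masking: "It is not permitted for any antiparkinsonian drug to be administered within 12 hours prior to DIEPSS assessment".

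Protocol 3.7.5.8 describes routine collection: "The investigator or subinvestigator will use DIEPSS at scheduled time points to assess the following 9 items". Its eCRF instruction belongs to that description and does not mention the assessment called for in 4.3.

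On analysis, SAP 3.4 states: "Nominal time points will be used for summary of safety parameters and plasma concentration". For DIEPSS, SAP 9.7.1 plans only that descriptive "statistics of actual measurements and changes from baseline at each time point will be produced". SAP Appendix 4 lists one mean-change DIEPSS table per cohort (CT-13.1.1 to CT-13.1.3) and no other DIEPSS summary. For concomitant drugs, SAP 7.5 says: "Listing of prior and concomitant medication will be presented". SAP Appendix 5 adds subject-level listings of DIEPSS (PDATA-13) and of concomitant medications (PDATA-6.1).

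**The concern.** The assessment in protocol 4.3 is prompted by symptoms, so it can fall on any day. It may also be the most informative DIEPSS a subject has, because it is taken when the investigator has decided that treatment is needed and before that treatment starts. If it falls between visits, the planned summaries skip it and pick the subject up at the next scheduled visit, by then on an antiparkinsonian drug and with nothing in the table to say so.

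The cohorts are uncontrolled and planned at 20 subjects each. The QW formulation is given on top of background antipsychotics of up to 600 mg/day chlorpromazine-equivalent. In that setting the extrapyramidal signal may rest on a few people. A table of by-visit means could look quiet while the adverse event tables show treated extrapyramidal symptoms, and no planned DIEPSS output would reconcile the two.

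**Working it through.** The documents give no figure to reproduce. The check is of the text, then of direction, then of what can be said about size.

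**1. Is the off-visit score picked up anywhere?**
- SAP 3.4 and 9.7.1: nominal time points only, with no rule for unscheduled DIEPSS.
- SAP Appendix 4: mean-change tables only, with no worst post-baseline score.
- SAP section 9: a rule that takes every value in the period exists, but only for potentially clinically significant abnormalities. Those criteria (Appendices 1 to 3) cover laboratory values, vital signs, weight and ECG, not DIEPSS.
- SAP 7.5: antiparkinsonian use is listed, not counted.
- SAP Appendix 5: PDATA-13 would show the score if it was entered.

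So the score reaches a listing at best, and no summary.

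**2. Is there room between visits?** The schedule tables are broken in the text available, so these are readings.
- Cohort 2, Period 2 (protocol Table 3.7-2): DIEPSS on Days 1, 4, 8, 11, 15, 22, 29, 36 and 42. The gaps are 3, 4, 3, 4, 7, 7, 7 and 6 days.
- Cohort 1, each QW period (Table 3.7-1): predose and Days 4, 8 and 14. The gaps are 3, 4 and 6 days.

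A symptom-driven assessment can fall off schedule, but it can also coincide with a scheduled one, in which case it is tabulated.

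**3. Direction.** For one subject in one period, let S be the scheduled post-baseline assessments and A all post-baseline assessments. S is contained in A, so

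max(S) ≤ max(A).

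A summary built on S can equal or fall below the subject's worst score and cannot exceed it. This needs no assumption about how well rescue works. It concerns the worst score only: a mean at a given visit still describes correctly what was observed at that visit.

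**4. Size, as illustration only.** Suppose k of 20 subjects have an off-visit score that exceeds their highest scheduled score by g points. The cohort mean of the worst score is then understated by k × g / 20. Neither k nor g is in the documents. Assumed values give:
- k = 1, g = 1: 0.05 points
- k = 3, g = 2: 0.30 points
- k = 4, g = 4: 0.80 points

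The nearest figures for k are adverse event rates on the conventional tablet (protocol 1.2.2), which are not rescue rates:
- QT trial, 12 mg: akathisia 5/67 and extrapyramidal disorder 5/67. Expected per 20: 20 × 5/67 = 1.49 for one term, or 20 × 10/67 = 2.99 if no subject had both. Chance of at least one: 1 − (62/67)^20 = 0.79, or 1 − (57/67)^20 = 0.96.
- US multiple-dose trial, up to 12 mg: akathisia 2/48. Expected per 20: 20 × 2/48 = 0.83. Chance of at least one: 1 − (46/48)^20 = 0.57.

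The QT-trial rates come from higher peaks: mean Cmax 462 ng/mL, against a simulated 176 ng/mL for QW 48 mg (462/176 = 2.6). They may therefore overstate k here.

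**The case against.** The strongest reply is that this is a silence, not an exclusion. No sentence in the SAP bars unscheduled scores. Protocol 4.3 asks for the assessment before drug use, not immediately before it, so a scheduled DIEPSS on the day of starting would satisfy it. In Cohort 2, subjects are inpatients through Day 16, when DIEPSS gaps are only 3 to 4 days. Preventive antiparkinsonian use is prohibited, and the 12-hour hold limits masking. TEAEs are tabulated by system organ class, preferred term, severity, relatedness and onset week. With 20 subjects, PDATA-13 and PDATA-6.1 can be read line by line. The primary and secondary outcomes are pharmacokinetic, and neither progression to Cohort 2 nor the withdrawal criteria before dose increase use a DIEPSS threshold.

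Most of this stands, and it is why the point is modest. It does not close the gap. Adverse event terms carry no DIEPSS score, a listing is not a summary, and the listing helps only if the score was entered.

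A reader might go further and infer that the mean change is biased toward no effect by a known amount. The documents do not support that. They do not say how often rescue occurs, how far scores fall afterwards, or that a 12-hour hold is inadequate.

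**Conclusion.** The point holds as a cheap improvement. As written, the DIEPSS summary tables omit an off-visit pre-rescue score and do not mark later scores on rescue, so they can match or understate a subject's worst extrapyramidal score but never overstate it. The omission follows from nominal time points combined with silence on unscheduled scores. The direction is certain for the worst score. The size is unknown, and the 0.05 to 0.80 points above rests entirely on assumed k and g. No dosing or progression rule turns on it.

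It might also be inferred that scores after rescue, or after a reduction of background antipsychotic, should be removed from the by-visit means. That does not follow. It would take symptomatic subjects out of every later visit in a single-arm cohort of 20, which is informative exclusion and could itself push the mean toward no effect.

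**What to change.** In SAP 9.7.1 and tables CT-13.1.1 to CT-13.1.3:
- Add, for each QW period of Cohort 1 and Cohort 1' and for Cohort 2, the highest post-baseline DIEPSS total and item scores and their change from baseline. Use all assessments, including unscheduled ones taken before antiparkinsonian use.
- Show in the same table the number of subjects who started or increased an antiparkinsonian drug.
- Keep the by-visit means as observed; at most, flag scores taken after such a start or increase, or after a background antipsychotic reduction.

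Make sure the eCRF takes the unscheduled scores. The eCRF is not among the documents, so it may already do so. If the sponsor prefers to state this in protocol 3.7.5.8, that wording needs an amendment under protocol section 13.

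The cost is one extra table block and an eCRF entry, with no new procedure and no change to any treatment rule. The reported maximum may look slightly less favourable.

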9.7.2 C-SSRS

The number and percentage of subjects with each C-SSRS item (suicidality, suicidal ideation, suicidal behavior, completed suicide, emergence of suicidal ideation, emergence of serious suicidal ideation, worsening of suicidal ideation, and emergence of suicidal behavior) at each time point will be determined.

The definitions for each assessment other than completed suicide are defined as follows.

- 1) Suicidality: Defined as reporting any suicidal ideation or behavior
- 2) Suicidal ideation: Defined as reporting any type of suicidal ideation
- 3) Suicidal behavior: Defined as reporting any type of suicidal behavior
- 4) Emergence of suicidal ideation: Defined as having no suicidal ideation at baseline and reporting any type of ideation at postbaseline
- 5) Emergence of serious suicidal ideation: Defined as having no suicidal ideation at baseline and reporting serious suicidal ideation with a score of 4 or 5 on the suicidal ideation severity rating at postbaseline
- 6) Worsening of suicidal ideation: Defined as having a more severe rating in suicidal ideation rating assessment at postbaseline than at baseline
- 7) Emergence of suicidal behavior: Defined as having no suicidal behavior at baseline and reporting any type of behavior at postbaseline

10 Pharmacokinetic Analyses

10.1 Statistical Analyses of Primary and Secondary Pharmacokinetic Endpoints

The PK parameters of brexpiprazole (OPC-34712) for the QW formulation and conventional tablet at each dose will be determined using noncompartmental PK analysis. Descriptive statistics of the following variables will be produced.

10.1.1 Brexpiprazole QW Formulation

10.1.1.1 Period 2 of the Single Administration Period (Cohort 1 and Cohort 1' [as Necessary])

- 1) Plasma concentration of OPC-34712 after a single administration of the QW formulation
- 2) PK parameters of OPC-34712 after a single administration of the QW formulation C_{max}, t_{max}, t_{last}, C_{max}/D
- Relative C_{max} of OPC-34712 for the QW formulation as compared with a conventional tablet Relative C_{max} (%)

= (C_{max} of QW formulation/dose of QW formulation)/(C_{max} of conventional tablet/dose of conventional tablet) × 100

10.1.1.2 Period 3 of the Single Administration Period (Cohort 1 and Cohort 1' [as Necessary])

- 1) Plasma concentration of OPC-34712 after a single administration of the QW formulation
- PK parameters of OPC-34712 after a single administration of the QW formulation C_{max}, AUC_∞, AUC_t, t_{max}, λ_z, AUC_%Extrap, t_{1/2,z}, CL/F, CL/F/BW, t_{last}, C_{max}/D, AUC_∞/D, AUC_t/D
- 3) Relative bioavailability of OPC-34712 for the QW formulation as compared with a conventional tablet Relative bioavailability (%)
 = (AUC_∞ of QW formulation/dose of QW formulation)/(AUC_∞ of conventional tablet/dose of conventional tablet) × 100
- 4) Relative C_{max} of OPC-34712 for the QW formulation as compared with a conventional tablet Relative C_{max} (%)

= (C_{max} of QW formulation/dose of QW formulation)/(C_{max} of conventional tablet/dose of conventional tablet) × 100

